6.7 Secondary Analyses

All analysis of secondary endpoint will be interpreted purely exploratory. For all hypotheses two-sided exploratory p-values will be provided. Descriptive statistics will be displayed for all.

6.7.1 Efficacy

For both, START and STOP HCQ blocks absolute and relative change under the active compound from trial day 1, i.e. Visit 2, to START block: day 28, day 56 STOP block: day 84 each, will be compared between treatment groups .

The following variables will be investigated:

- Oxygen saturation (O2-sat, in room air) (only absolute, as relative already primary outcome)
- Respiratory rate (RR, in room air) (relative and absolute)
- Retractions (yes/no)
- Coughing last 24 h (yes/no)
- Oxygen requirement (yes/no)
- pO2, pCO2 (capillary, in room air)
- Chest x-ray scoring for chILD
- Overall survival (time from randomization until death; if no death observed, time will be censored at time point of last (follow-up-)visit): a Kaplan-Meier plot will be provided; if possible, the median overall survival and corresponding 95%-confidence interval will be calculated
- Cumulative amounts of steroid equivalents per time period
- If > 5 y old
 - FEV1 % predicted (recorded in L)

- FVC % predicted (recorded in L)
- reference values according to the GLI 2012 lung function regression equations
- 6 minutes walking distance (meter)
- O2-saturation before and after 6MWT
- If ventilated:
 - Duration (h) of mechanical ventilation
 - NO (%), ECMO yes/no, if yes VA/VV, double lumen vs. single lumen, Flow-rate.

Additionally, FEV₁, FVC, FVC predicted, 6 min walking distance will be displayed by Box-Plots and All-in-one plots over each time point.

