Statistical analysis	START HCQ block and STOP HCQ block The variable assessing the primary outcome is the response rate measured by the oxygen saturation in room air. Both blocks separately a) A difference between the changes in placebo and active phases is considered significant, if the oxygen saturation increases by $\geq 5\%$ . b) Patients are defined as responder if the oxygen saturation is increased by 5% compared to baseline. The numbers of responders are counted and compared by Fisher exact test. Both blocks together c) oxygen saturation and the correspondent responder will be analysed by a linear mixed model (or logistic regression respectively). If indicated, a Bayesian approach will be employed. If appropriate, the analyses will be adjusted for the stratification factor of the randomization: age group.

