4.2.1 Efficacy

The following variables will be investigated:

- Oxygen saturation (O2-sat, in room air) (only absolute, as relative already primary outcome) assessed at every visit (not web/tele feedback)
- Respiratory rate (RR, in room air) (relative and absolute) assessed at every visit and every web/tele feedback
- Retractions (yes/no) assessed at every visit and every web/tele feedback
- Coughing last 24 h (yes/no) assessed at every visit and every web/tele feedback
- Oxygen requirement assessed at every visit and every web/tele feedback
- pO2, pCO2 (capillary, in room air)
- Chest x-ray scoring for chILD assessed at screening and visit 3 (START HCQ Block) and visit 5 (STOP HCQ Block)
- Overall survival
- If > 5y old
 - FEV1 % predicted (recorded in L)
 - FVC % predicted (recorded in L)
 - reference values according to the GLI 2012 lung function regression equations
 - 6 minutes walking distance (meter)
 - O2-saturation before and after 6MWT
 - Borg scale
- If ventilated:
 - Duration (h) of mechanical ventilation
 - NO (%), ECMO yes/no, if yes VA/VV, double lumen vs. single lumen, Flow-rate.

4.2.2 *Safety/Tolerability*

Adverse events, clinical laboratory values (GOT, Creatinine, gGT, blood count, differential, LDH, BNP, steady state drug level), ECG, ophthalmologic review

Adverse events will be documented during the study at each visit (exemption: START HCQ between Visits 1 and 2. However, occurring AEs between those visits are not treatment emergent).

Laboratory data will be assessed at screening, visit 3 and visit 4 in the START HCQ Block and at screening, visit 3, 4 and visit 5 and EDTA additionally at visit 6 in the STOP HCQ Block.

Vital signs (respiratory rate, height, weight, BMI, heart rate, blood pressure (systolic and diastolic), temperature, hypoglycaemia (yes/no), appropriate observation of blood glucose levels (yes/no), cardiotoxicity (yes/no), appropriate ECG (yes/no)) will be assessed at screening, and every following visit (not web/tele feedback).

A physical examination will be done at the same visits.

Symptoms and clinical course of treatment will be documented at the same time points as the physical examination is performed and at telephone contact visit.

4.2.3 *Quality of Life (Peds QL)*

Not applicable.

4.2.4 *Health Economics*

Not applicable.

5 Treatment of Missing Values and Outliers

5.1 *Missing Values*

No substitution of missing values is planned.

5.2 *Outliers*

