There will be no methods employed for detecting outliers.

6 Statistical Analyses

The default summary statistics for quantitative variables will be the number of observations (n), mean, standard deviation (SD), median, first quartile (Q1), third quartile (Q3), minimum and maximum for those patients with data available.

For qualitative variables, the number (n) and percentage (%) of patients with non-missing data per category will be the default summary presentation. If appropriate, the number of missing values will be displayed as a “Missing” category.

A value will be considered missing if a patient attends the visit (visit date is available) but no value is documented.

All variables will be displayed by treatment group and with a total column.

Listings of all AE data available will be provided only.

6.1 *Patient Disposition*

The following patient disposition variables will be presented by numbers and percentages:

- Informed consent given to study participation / study treatment
- Inclusion and exclusion criteria

- Size of analysis populations (enrolled, ITT, safety)
- Study completion according to protocol
- Reasons for premature discontinuation of study treatment
- Type of major protocol violation

Protocol deviations which are documented in the CRF will be listed additionally.

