6.6 Primary Analysis

The variable assessing the primary outcome is the response rate measured by the oxygen saturation in room air.

START HCQ block

Relative change from trial day 1 (Visit 2) to day 28 (Visit 3) and day 56 (Visit 4) and from day 28 to day 56 change from active compound compared to change from placebo

STOP HCQ block

Relative change from trial day 1, i.e. Visit 2, through day 84, i.e. Visit 5: change from active compound compared to change from placebo

Both blocks separately

a) A difference between the changes in placebo and active phases is considered significant as described in the table below.

Patient's condition	Measured parameter	Definition of significant change or responder
Stable in room air or on	SpO2 in room air	Increase $\geq 5\%$

O2-supplement		
On high-flow nasal cannula	O2-flow, air-flow	Decrease $\geq 20\%$ or support not needed any more
Ventilated	Oxygenation index	Decrease $\geq 20\%$ or support not needed any more
On ECMO		Decrease $\geq 20\%$ or support not needed any more

The analysis will be done first by discarding the information on the patient's condition. Descriptive analyses will be done overall and for all patients conditions separately.

b) Patients are defined as responder as described in the table above. The numbers of responders are counted and compared by Fisher's exact test as well as logistic regression models with factors for treatment group and age group.

The following SAS code can be used:

```
PROC LOGISTIC DATA=indata;
  CLASS treatment age_gr;
  MODEL responder_YN = treatment age_group treatment*age_group;
RUN;
```

Both blocks together

Not applicable. There were too few patients in both blocks.

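### STOP: room-air SpO2 is scheduled at days 28, 56 and 84, but the between-arm comparison uses day 84 alone, so a child with no Visit 5 value drops out of it

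*SAP*

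**What the plan says.** - **Measurement.** SAP 4.2.1 has SpO2 "assessed at every visit (not web/tele feedback"). In the SAP's STOP schedule, the clinic visits under blinded treatment are Visits 3, 4 and 5, at days 28, 56 and 84. The protocol's Table 1-2 agrees.
- **Time point analysed.** For STOP, SAP 6.6 takes "Relative change from trial day 1, i.e. Visit 2, through day 84, i.e. Visit 5". SAP 6.7.1 does the same for the secondary outcomes: "STOP block: day 84 each, will be compared between treatment groups". Protocol 3.3, 3.4 and 8.3.1 also name day 84 alone.
- **Methods.** SAP 6.6 gives Fisher's exact test and a logistic model with treatment, age group and their interaction. Neither has a visit term. SAP 6.7.1 names no test for the continuous SpO2 change.
- **Missing data.** SAP 5.1: "No substitution of missing values is planned". Under SAP 6, summaries are "for those patients with data available". No rule classes a child with a missing value as a non-responder.
- **Combined analysis.** The protocol synopsis, in the item covering both blocks jointly, says "oxygen saturation and the correspondent responder will be analysed by a linear mixed model". SAP 6.6 withdraws that item: "Not applicable. There were too few patients in both blocks".

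**The concern.** A child with SpO2 at Visit 2, day 28 and day 56 but not at Visit 5 has no day-84 change and no responder status. The child stays in the ITT population on paper but drops out of the planned between-arm SpO2 comparison, and the two earlier readings are not used there.

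This matters in a withdrawal design because leaving may be tied to the outcome. The withdrawal criteria in protocol 3.6.3 include life-threatening worsening of the disease, a need for interfering drugs and other medical reasons. Protocol 4.2 expects that some patients will deteriorate, and withdrawn subjects are not replaced. If stopping HCQ does harm, more placebo children may be missing at day 84, and those who remain are the better ones. The observed difference then shrinks toward zero.

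**Working it through.** **Inputs from the documents.** The target is 80 patients (protocol 8.1), split equally between blocks (protocol 3.2) and allocated 1:1 (protocol 3.5.1). STOP therefore has 80 / 2 / 2 = 20 per arm. Protocol 8.1 gives no sample size calculation, so there is no power figure to reproduce. Effect size, SD, dropout rate and between-visit correlation are not stated, and every value below is an assumption.

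**Step 1: precision, if dropout is unrelated to outcome.** Let d be the share lost after day 56, n = 20(1 − d) the completers per arm, ρ the correlation of the day-84 value with its prediction from earlier visits, and 0.8 SD the true difference (two-sided 0.05).

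- Completers only: SE² = 2/n.
- Model using the earlier visits (large-sample formula for monotone missing data): SE² = (2/n)(1 − ρ²d).
- Example, d = 0.2 and ρ = 0.7: (2/16)(1 − 0.49 × 0.2) = 0.125 × 0.902 = 0.1128. So SE = 0.336, equivalent to 2/0.1128 = 17.7 per arm instead of 16.

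| d | Completers per arm | Power, completers | Effective per arm, model (ρ 0.5–0.8) | Power, model |
|---|---|---|---|---|
| 0 | 20 | 0.72 | 20 | 0.72 |
| 10% | 18 | 0.67 | 18.5–19.2 | 0.68–0.70 |
| 20% | 16 | 0.62 | 16.8–18.3 | 0.64–0.68 |
| 30% | 14 | 0.56 | 15.1–17.3 | 0.60–0.65 |

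The gain in precision is modest.

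**Step 2: bias, if children who are worse leave more often.** Two sets of 4,000 simulated trials per scenario, 20 per arm:

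- *Set A.* True difference 0.80 SD. The chance of leaving after day 56 rises as the day-56 value falls (logistic). Overall dropout 10 to 30%, ρ 0.5 to 0.8. Loss was 6–22% on HCQ and 14–38% on placebo. Completers gave 0.747 down to 0.664 SD, an attenuation of 1 − 0.747/0.80 = 6.6% up to 1 − 0.664/0.80 = 17.0%. The likelihood estimate using days 28 and 56 gave 0.79–0.81 SD.
- *Set B.* True day-84 difference −3 SpO2 points, SD 4, AR(1) correlation 0.6 or 0.8. Probability 0.5 or 0.8 of leaving after an observed fall of more than 4 points at day 28 or 56. Loss was 8–21% on HCQ and 18–33% on placebo. The observed-case change difference was −2.4 to −2.7 (11–20% attenuation), observed-case ANCOVA gave −2.6 to −2.8, and the repeated-measures likelihood estimate gave −3.0.

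**Step 3: bias against noise.** In Set A the bias is 0.80 − 0.747 = 0.053 to 0.80 − 0.664 = 0.136 SD, while the completer estimate varies between trials with SD 0.32–0.37. The model's estimate varies about as much (0.32–0.37). In Set B the bias is 0.3–0.6 points. With SD 4 and 16 completers per arm, the standard error is about 4 × √(2/16) = 1.4 points. The benefit is mainly less bias rather than a tighter interval.

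**The case against.** Two stronger readings are tempting, and the documents do not support either.

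- *A reader might infer that the SAP removed a repeated-visit model.* It did not. The protocol's mixed model belongs to the analysis of both blocks together, with no visit term or repeated-measures structure stated. The SAP's reason, "There were too few patients in both blocks", fits the analysis it withdraws. No longitudinal model within STOP was ever planned, and day 84 alone is the protocol's own contrast.
- *A reader might infer that all earlier-visit data are discarded.* Respiratory rate is listed among the vital signs at every visit (SAP 4.2.2), and changes from baseline are analysed with exploratory p-values (SAP 6.7.2.3). FEV1 and FVC are plotted at each time point (SAP 6.7.1). A child who leaves early still counts for safety and survival. The gap concerns SpO2.

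Other objections have weight:

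- The trial is exploratory. Protocol 8.3.1 makes the primary outcome dichotomous and uses SpO2 continuously only as a descriptive secondary outcome. This limits the point to a supportive analysis.
- Protocol 3.6.3 asks for the final-day examinations at withdrawal where possible, so some early leavers may have a late reading. The SAP does not say whether such a reading counts as day 84, so this helps only in part.
- Both simulation sets let dropout depend only on observed values, the condition under which the likelihood model is unbiased. They show what the model can do, not what will happen here. Protocol 1.3 gives a half-life of 30 to 60 days, so falls could come late or between visits, where earlier readings predict less.
- The SAP records room-air readings under 80% as a category, which a normal model cannot use. Children on high flow or ventilation are assessed on other measures. Unstructured covariance is fragile at this size.

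These shape the model but do not remove the reason for it.

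**Conclusion.** The point holds for SpO2 in STOP. Readings at days 28 and 56 are scheduled but play no part in the planned between-arm comparison, and a child without a Visit 5 value is lost from it. If worsening drives dropout, the observed-case difference is attenuated by about 7 to 20%. That range rests wholly on assumed dropout, SD, effect and correlation. The bias is well below the sampling error at about 20 per arm, so this is a worthwhile improvement and not a flaw that invalidates the block. START is not affected in the same way, because day 28 is its only clinic visit before placebo patients switch to HCQ.

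**What to change.** In SAP 6.7.1, for the secondary continuous SpO2 outcome in STOP, add a mixed model for repeated measures at days 28, 56 and 84, restricted to patients assessed by room-air SpO2:

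- Fixed effects: treatment, visit, treatment-by-visit, Visit 2 value and age group.
- REML with Kenward-Roger degrees of freedom. Start with unstructured covariance and name in advance a simpler structure, such as AR(1), for use if it does not converge.
- Report the day-84 contrast with its 95% CI, and list deaths separately.
- Use the exact SpO2 value that footnote e of the protocol's visit schedule asks for, in place of the SAP's below-80% category.
- State to which scheduled visit, if any, an early final examination is assigned.

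The Fisher and logistic responder analyses stay as planned. They will still omit children without a Visit 5 value, and this model does not change that.

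The cost is a paragraph of SAP text and one SAS procedure on data already scheduled. The downside is reliance on a covariance structure and on missingness at random with about 20 per arm.

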### 3.6.3 *Withdrawal criteria*

Subjects or/and representatives can withdraw their consent at their own request without given reasons at all time during the trial. This should be without disadvantages for the subject. However the investigator should try to perform a final visit to get concluding findings of investigation.

Subjects may be withdrawn from the trial for the following reasons

- At their own request or at request of the legal representative.
- At the instigation of the sponsor. If, in the investigator's opinion, continuation of the trial would be detrimental to the subject's well-being.
- For women, if it becomes known that the subject is pregnant.
- Aggravation of disease with life threatening events
- Severe side effects (for example retinopathy, cardiomyopathy, ECG-modifications, liver value elevation)
- The subject/ patient is non-compliant or uncooperative
- The subject/ patient is not able to participate due to an Adverse Event
- The subject/ patient has to take any concomitant drugs interfering with the study medication
- The subject/ patient is no longer able to participate for other medical reasons (e.g., surgery, other diseases, or death)

The investigator decides about withdrawal of subjects from the clinical trial in case of occurrence of criteria mentioned above.

In all cases, the reason for withdrawal must be recorded in the CRF and in the subject's medical records. In case of withdrawal of a subject at his/her own request, as far as possible the reason should be asked for and documented. The subject must be followed up and as far as possible; all examinations scheduled for the final trial day should be performed and documented and all trial medication should be collected at site.

All on-going serious adverse events of withdrawn subjects have to be followed up see 7.3.

Withdrawn subjects will not be replaced.

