## 7 Safety

### 7.1 Definitions

#### Adverse Event (AE)

According to GCP, an adverse event (AE) is defined as any untoward medical occurrence in a subject treated with a pharmaceutical product and which does not necessarily have a causal relationship with this treatment. An AE can be any unfavourable and unintended sign (including an abnormal laboratory finding), symptom, or disease temporally associated with the use of a medicinal (investigational) product, whether or not related to the medicinal (investigational) product.

An AE may be:

- a new symptom or a new diagnosis
- a new medical condition or an accident
- a change in laboratory parameters
- an intercurrent illness or accident
- worsening of a medical condition/diseases existing before the start of the clinical trial
- recurrence of a disease
- an increase in frequency or intensity of episodic diseases.

Surgical procedures themselves are not AEs; they are therapeutic measures for conditions that require surgery. The condition for which the surgery is required may be an AE. Planned surgical measures permitted by the clinical trial protocol and the condition(s) leading to these measures are not AEs, if the condition leading to the measure was present before inclusion in the trial. In the latter case the condition should be reported as medical history.

Change in laboratory parameters: The criteria for determining whether an abnormal test finding should be reported as an adverse event are as follows:

- Test result is associated with accompanying symptoms, and/ or
- Test result requires additional diagnostic testing or medical/ surgical intervention, and/ or
- Test result leads to a change in trial dosing outside of protocol-stipulated dose adjustments, or discontinuation from the trial, significant additional concomitant drug treatment, or other therapy, and/ or
- Test result is considered to be an adverse event by the investigator or sponsor.
- Progression of child under treatment should not be reported as an adverse event. However, if child leads to a fatal outcome during the trial or within the safety reporting period, then disease progression should be reported as an adverse event and as a serious adverse event with outcome “death”.

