### 7.3 Period of observation

In this trial, the period of observation for collection of adverse events extends from signing the informed consent up to the end of trial. If the investigator detects a serious adverse event in a trial subject after the end of the period of observation, and considers the event possibly related to the prior trial, he should contact the sponsor to determine how the adverse event should be documented and reported.

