### 7.4 Documentation of AEs and Follow up

All AEs (whether serious or not) reported by the subject or detected by the investigator will be documented on the appropriate pages of the case report form (CRF). AEs must also be documented in the subject's medical records. If the adverse event is serious (see Section 7.1), the investigator must complete, in addition to the "Adverse Event Page", a "Serious Adverse Event Form" at the time the serious adverse event is detected.

Every attempt should be made to describe the adverse event in terms of a diagnosis. If a clear diagnosis has been made, individual signs and symptoms will not be recorded unless they represent atypical or extreme manifestations of the diagnosis, in which case they should be reported as separate events. If a clear diagnosis cannot be established, each sign and symptom must be recorded individually.

All subjects who have adverse events, whether considered associated with the use of the investigational products or not, must be monitored to determine the outcome. The clinical course of the adverse event will be followed up according to accepted standards of medical practice, even after the end of the period of observation, until a satisfactory explanation is found or the investigator considers it medically justifiable to terminate follow-up, but no longer than 90 days after the end of the trial.

Should the adverse event result in death, a full pathologist's report should be supplied, if possible.

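### SAP 6.7.1 sets no end date for counting deaths but censors survivors at their last visit, so one late death in a START arm can take the survival curve to 0%

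*SAP*

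**What the plan says.** SAP 6.7.1 defines the variable as "Overall survival (time from randomization until death" and gives no upper time limit. For patients without a death the rule is "if no death observed, time will be censored at time point of last (follow-up-)visit". A Kaplan-Meier plot is to be provided, and "if possible, the median overall survival and corresponding 95%-confidence interval will be calculated".

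Protocol 8.3.2 is more cautious. It plans a Kaplan-Meier plot only when a reasonable number of events occur. The SAP drops that condition.

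The protocol's safety sections decide which later deaths could become known:

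- **Section 7.3:** "the period of observation for collection of adverse events extends from signing the informed consent up to the end of trial". The same section continues: "If the investigator detects a serious adverse event in a trial subject after the end of the period of observation", and considers it possibly related, the sponsor is contacted to settle how it is documented. No time limit is given.
- **Section 7.4:** adverse events are followed after the observation period until explained or until stopping is medically justifiable, "but no longer than 90 days after the end of the trial".
- **Section 7.1:** disease progression that "leads to a fatal outcome during the trial or within the safety reporting period" is reported as a serious adverse event with outcome death.
- **Section 3.6.3:** "All on-going serious adverse events of withdrawn subjects have to be followed up".

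The last scheduled contact is Visit 4 in START (day 56, window -4 to +7) and the day-168 follow-up in STOP (window ±7). Both schedules label START Visit 4 and STOP Visit 5 (day 84) as the end of trial.

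**The concern.** Kaplan-Meier estimation needs follow-up that does not depend on the outcome. Here a death counts whenever it is observed, while survival counts only up to a visit. The extra follow-up is also selective. It reaches children with an adverse event still being followed, or with a late event judged possibly related. No passage schedules a vital-status check of the other children in that period, and none says that a death after the last visit is left out of overall survival.

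After the last scheduled visits the risk set can therefore shrink to the child who died. The curve then shows nobody surviving in an arm where nearly everyone is alive, and it yields a median that describes one child. In a placebo-controlled trial, mostly in children, a reader weighing safety could be misled by that plot.

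**Working it through.** The documents give no survival figure, expected mortality or event target to reproduce. The check is what the stated rule does.

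**Inputs.** The plan is 80 subjects (SAP 1.2), an equal split between blocks and 1:1 allocation (Protocol 3.5.1). That is 80 / 2 / 2 = 20 per arm per block. Randomisation falls in the screening window: day -28 to -3 in START, day -30 to -10 in STOP. The last visit is day 52 to 63 in START and day 161 to 175 in STOP.

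**Time scale.** With no day 0, a child randomised on day -r reaches trial day d after r + d - 1 days. Counting a day 0 adds one day throughout.

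| Block | Completers censored, days from randomisation | Own last visit + 90 days |
|---|---|---|
| START | 3 + 52 - 1 = 54 to 28 + 63 - 1 = 90 | 144 to 180 |
| STOP (day-168 visit) | 10 + 161 - 1 = 170 to 30 + 175 - 1 = 204 | 260 to 294 |

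**START, death on day 100.** It falls between 3 + 100 - 1 = 102 and 28 + 100 - 1 = 127 days after randomisation, always later than the last possible censoring at 90. One child is at risk, so S = 1 - 1/1 = 0 and the median is that death time.

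**Worked case.** All 20 children are randomised on day -28 and seen on day 56. Nineteen are censored at 28 + 56 - 1 = 83 days. One dies 30 days later, at 113 days.

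- SAP rule: S = 0%, median 113 days.
- Vital status known for all to Visit 4 + 90 days: S = 19/20 = 95%, median not reached.
- Common cut-off at Visit 4: S = 100%, with the death reported outside the curve.

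**How often, given one such death.** This is a simulation with visit and randomisation days uniform in their windows and the death uniform over the 90 days after that child's own last visit. S reaches 0% in about 85% of START arms of 20 and about 86% of STOP arms of 20. S falls to 50% or below, which fixes the median, in about 87% and 88%. These percentages depend on the assumed timing. That S can reach 0% does not.

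**STOP and the meaning of end of the trial.** If it means the day-168 visit or later, the table applies. If it means Visit 5, the 90 days end at day 84 + 90 = 174, inside the last-visit window of 161 to 175. Little exposure through Protocol 7.4 is then left: S reaches 0% in about 7% of simulated arms of 20 with a death between the last visit and day 174. Protocol 7.3 has no such limit. A START child is exposed on either per-patient reading, since Visit 4 is both the last visit and the labelled end of trial.

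**Would a cut-off by trial day repair it?** No, because the clock starts at randomisation. With deaths counted to day 63 (START) or day 175 (STOP), and one death on exactly that day, S is still 0% in about 16% and 19% of arms of 20. It is 0% in about 94% when that child had the longest screening gap. A cut-off on the randomisation clock at the shortest completer time avoids this: 54 days in START, 170 in STOP. Every completer is still at risk then.

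**The case against.** The case for leaving the rule alone has real substance.

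- **No one-event curve was intended.** Protocol 8.3.2 would show no curve for a single death, and the SAP's median is conditional. The first part supports restoring the condition, because SAP 6.7.1 now says the plot will be provided. The second gives no protection: the late death is what makes the median calculable.
- **The link from safety data to this variable is inferred.** Nothing says that a death learned through adverse-event follow-up enters the survival dataset, and the 90 days are a maximum for events still being followed. This stands as a limit on likelihood. The definition still takes any observed death and excludes none.
- **The follow-up visit may include adverse-event contacts.** If m other children were still followed, S = 1 - 1/(m + 1): 50% with one other, 80% with four. The SAP does not say this.
- **Consequences are small.** SAP 6.7 treats all secondary analyses as exploratory, and SAP 6.7.2.1 plans an overview row for patients with any deaths and a listing of all adverse events. This stands and sets the severity.

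A reader might infer three stronger things. One is that STOP behaves like START without qualification; that depends on an undefined term. Another is that following withdrawn children's serious adverse events materially biases the curve. In an assumed example, 6 of 20 withdraw and are censored, and 2 of those 6 later die. This gives 1 - 2/16 = 87.5% against 18/20 = 90%, which is small beside a standard error of about 8 points. Protocol 3.6.3 also asks that withdrawn subjects be followed up, so censoring at withdrawal is not stated. The last is that the trial's efficacy conclusion is at risk; the primary outcome does not use survival.

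**Conclusion.** The concern holds as a minor defect in the stated rule. In START, one observed death after the other children in the arm are censored (at most about 90 days after randomisation) gives an estimate of 0% and a median equal to that death time, when 19 of 20 are alive. In STOP the same general exposure exists only if the end of the trial in Protocol 7.4 means day 168 or later, or if the death arrives through Protocol 7.3. On the Visit 5 reading little remains.

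This rests on three assumptions: about 20 children per arm, a late death that is entered in the survival dataset, and a follow-up visit that means a scheduled visit. The documents give no mortality figure, so the chance of such a death cannot be stated; the 85% and 86% are conditional on one having occurred. The effect is a misleading secondary plot and median.

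**What to change.** In SAP 6.7.1:

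1. End the Kaplan-Meier analysis at one fixed time after randomisation that every completer reaches: about 54 days in START and 170 days in STOP. Count only deaths up to that time.
2. Censor survivors at the earlier of that time and the date last known alive from any contact (visit, phone or email visit, adverse-event follow-up).
3. Report all deaths, including later ones, as counts by arm and in a listing.
4. Drop the median.
5. Restore the condition in Protocol 8.3.2 that a curve is shown only when a reasonable number of events occur.

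The cost is a few sentences of SAP text. The schedules already collect contact dates and record whether the patient died, so no new data are needed. The downside is that deaths after the cut-off appear only in the counts and listing. The curve also covers less of the block for a child with a long screening gap: with the longest gap it ends on trial day 54 - 28 + 1 = 27 in START and 170 - 30 + 1 = 141 in STOP. The change does not fully remove uneven follow-up among early withdrawals, since those with no later contact are still censored early.
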